1 INTRODUCTION

End Stage Renal Disease (ESRD) currently affects over 2 million people worldwide.¹ It is projected that the worldwide incidence of ESRD will increase dramatically over the next 10 years, due to the increasing incidence of an aging population, diabetes, hypertension, and obesity.² Currently, Renal Replacement Therapy for patients with ESRD consists of either hemodialysis or peritoneal dialysis. The rates of implementation of either hemodialysis or peritoneal dialysis vary widely per country. According to the United States Renal Data System (USRDS), in 2006 hemodialysis accounted for around 60% of Renal Replacement Therapy patients in the US, while peritoneal dialysis accounted for 6- 7% of patients in the US and the remainder is kidney transplant patients.²

Vascular access is a critical component in the care of patients undergoing hemodialysis. The three methods of long term vascular access available to a patient requiring hemodialysis are: an autogenous arteriovenous access or native arteriovenous fistula (AVF), a prosthetic arteriovenous graft (AVG) or a tunneled dialysis catheter.³ The AVF has been shown to be superior to AVG and superior to catheter access in terms of both mortality and morbidity.^{4,5} In fact, the focus of numerous initiatives worldwide has been to increase the implementation of AVF as the preferred method of vascular access in patients requiring hemodialysis. In 1997, the National Kidney Foundation Kidney Disease Outcomes Quality Initiative (KDOQI) guidelines were published to highlight the importance and to promote the increased placement of AVF.⁶ These guidelines and subsequent versions have stressed the importance of proactive identification of patients requiring hemodialysis, and have described procedures and quality initiatives to maximize access longevity. In 2006, the updated KDOQI Guidelines recommended that AVF be constructed in at least 65% of prevalent hemodialysis patients.⁷ In addition, the AV Fistula First Breakthrough Initiative (FFBI), a coalition lead by the Center for Medicare and Medicaid Services (CMS) has set a formal goal for AVF construction of 65% in prevalent patients by 2009.⁸ The Society for Vascular Surgery (SVS) has also approved and sponsored initiatives around the development and publication of reporting standards for hemodialysis access and the development of practice guidelines for hemodialysis access.⁹

An AVF is traditionally created during a surgical procedure under general anesthesia. A surgical incision is made in the forearm or upper arm, followed by identification of target arteries and veins for surgical connection. Frequently, prior to the procedure, the vessels are mapped using duplex ultrasound imaging, allowing for pre-operative vessel diameter measurement and vessel selection. Typically, the radial artery or brachial artery and the cephalic vein or basilic veins are selected. The target vessels are carefully dissected and mobilized, and the vein is transected. An arteriotomy is created, and an anastomosis is sewn between the vein and the artery. After completion, the flow is verified using palpation and ultrasound, and the incision is closed. Over the course of the following 1 - 3 months, the AVF gradually matures, that is, the vein dilates and accepts increased flow sufficient for hemodialysis.

Though there is widespread agreement that the AVF is the preferred method of vascular access, 28 – 60% of AVFs do not successfully mature and are rendered unusable for hemodialysis.^{10,12} This has unintended consequences for patients in immediate need of hemodialysis, since a tunneled dialysis catheter must often be placed. Catheters are associated with higher morbidity, mortality, and costs and are therefore considered a last resort.¹¹

To improve on these results, and decrease the invasiveness of the procedure, a new tool and method for creation of an AVF has been developed, called everlinQ system. The system uses two devices,

one inserted into an artery and the other inserted into a closely-positioned vein. The devices contain magnets that bring a pair of electrodes into alignment. Radiofrequency energy is delivered to the electrodes, cutting and/or coagulating the tissue between the electrodes, creating an AVF. The procedure is facilitated using fluoroscopy and ultrasound imaging, to assist in vessel selection and to verify creation of the AVF. Because the vessels are not dissected and not mobilized, leaving the surrounding tissues intact, the vessels do not need to be sewn together with a traditional surgical technique. This proposed method may facilitate the creation of AVF, while reducing the trauma to the patient and also potentially prevent future venous stenosis thought to arise from surgical trauma. In particular, the goal is to reduce the surgical manipulation of the blood vessels, particularly the veins in the arm, which typically exhibit intimal hyperplasia in surgical AVF. Intimal hyperplasia is believed to be a root cause of failure in surgical AVF and AVG, and this technology and method may help improve the patency and maturity of AVF in patients with ESRD.

This clinical pilot study is being conducted to evaluate everlinQ System when utilized to create an AVF.

1.1 Device Description

The TVA Medical everlinQ System that will be used in this study is an investigational device, and is not cleared by FDA or any competent authority for sale in the US or elsewhere.

The everlinQ device is a single-use disposable device. The everlinQ catheter system consists of two flexible, magnetic catheters. One (venous) catheter contains an electrode to deliver radiofrequency (RF) energy, and has a cord that is connected for a remote hand switch. The venous catheter and hand switch, along with a standard grounding pad, connect to a standard electrosurgical unit for the delivery of RF energy. The second (arterial) catheter is a flexible magnetic catheter that contains a backstop for the RF electrode of the venous catheter to interface. Once the catheters are properly inserted and aligned, the magnets contained in each catheter attract to one another, approximating the vessels while simultaneously aligning the electrode with the backstop. RF energy is delivered to the electrode whereby the arterio-venous fistula (AVF) is created.

For additional details regarding device or its principal of operation, please refer to the most current Instruction for Use (IFU).

2 RISKS/BENEFITS

2.1 Benefits

The everlinQ System may facilitate a less-invasive and more reproducible AVF procedure. The everlinQ System may allow the physician to cut and coagulate soft tissues for the creation of an AVF while minimizing surgical incisions. Due to the less-invasive nature of the procedure with the everlinQ System, the AVF may exhibit improved maturation and patency characteristics compared to historical maturation and patency data. In addition, patient recovery time may be decreased, procedural time may be decreased, and anesthesia may be minimized compared to a conventional surgical AVF procedure.

2.2 Risks

Many of the potential risks and complications associated with the everlinQ System and procedure are similar to the risks expected for CKD patients undergoing surgically created arteriovenous fistula (AVF) procedures. The potential risks related to the everlinQ System and procedure are similar to surgical AVF creation and may include but not limited to:

- Bruising
- Numbness, tingling and/or coolness in the fistula extremity
- Occlusion/stenosis (AVF clots)
- Thrombosis (AVF completely clotted and cannot be used)
- Failure to mature (AVF can never be used)
- Additional procedures (interventions)
- Venous hypertension (arm swelling)
- Aborted or longer procedure
- Swelling, irritation or pain
- Bleeding, hematoma (a solid swelling of clotted blood within the tissues) or hemorrhage (an escape of blood from a ruptured blood vessel)
- Wound problem
- Fever (pyrogenic reaction)
- Steal or ischemia (not enough blood flow to hand)
- Embolism (blood clot or device piece)
- Infection (local or in the blood (bacteremia))
- Increased risk of congestive heart failure (heart fails due to increased flow from AVF)
- Vessel, nerve or AVF damage or rupture
- Pseudoaneurysm (leaking hole in artery that forms blood clot on outside of it)
- Heart problems such as arrhythmias (abnormal beats) that can be caused due to high levels of potassium in the blood (mostly due to CKD and not the TVA device or procedure)
- Death (mostly due to CKD related complications not the TVA device or procedure)
- Burns
- Problem due to sedation or anesthesia
- Sepsis (systemic inflammatory reaction)
- Toxic or allergic reaction
- Electrocution

In addition, fistula infiltration injury due to needle cannulation of the fistula is also a known risk/event.

Most of these potential risks also exist for creation of standard (surgical) AVFs. There may also be other risks related to use of the everlinQ System and procedure that are not listed or that are not known at this time. This study will help characterize the adverse events associated with the everlinQ System.

2.3 Minimization of Risk

To minimize the risks, the everlinQ system has undergone pre-clinical testing. In addition, all Investigators participating in this clinical trial will be trained on the everlinQ procedure which will contribute to minimizing risks associated with the use of the device.

3 STUDY METHODOLOGY

3.1 Study Design

This is a prospective, single-center study to evaluate the everlinQ System when used to create an endoAVF in hemodialysis patients. A total of up to 50 subjects will be enrolled and will undergo an endoAVF creation procedure using the everlinQ System. All subjects will be followed for up to 12 months post index procedure based on Investigator's discretion.

3.2 Study Objective

The primary objective of this clinical study is to evaluate the safety and efficacy of using the everlinQ system for the creation of an endovascular AVF (endoAVF) in patients requiring hemodialysis.

3.3 Study Endpoints

Study endpoints will be summarized using descriptive statistics. There are no formal hypothesis tests associated with these endpoints.

- **Technical success:** Verification that an endoAVF has been created and remains patent 1-7 Days after the index procedure. Patency will be determined by experienced examiner as the presence of a bruit that is detected with stethoscope, or presence of thrill, or via Duplex Ultrasound, or via angiogram.
- **Fistula Maturation:** defined as endoAVF that is free of stenosis or thrombosis, with brachial artery flow of at least 500 ml/min and at least 4 mm vein diameter (as measured by duplex ultrasound) OR patient was dialyzed using 2 needles.
- **The Time to Fistula Maturation:** the number of days between the date of AVF creation and the date of endoAVF maturation (based on primary efficacy endpoint definition of maturation).
- **Duration of Central Venous Catheter Exposure:** The rate of CVC use per enrolled subjects at 30-45 Days and other follow-up visits. The analysis will be performed for pre-dialysis and on dialysis patients, as applicable.
- **EndoAVF-related Re-intervention Rate:** The re-intervention rate for endoAVF (defined as any intervention required to maintain or re-establish patency) will be calculated at each available follow-up visit post index procedure.
- **Primary Patency:** The primary patency rate will be determined via Kaplan-Meier methods and based on the time of endoAVF creation until any intervention designed to maintain or reestablish patency or endoAVF abandonment.
- **Secondary Patency:** The secondary patency rate will be determined via Kaplan-Meier methods and based on the time of endoAVF creation until access abandonment. Abandonment due to renal transplant receipt will not be included in this endpoint assessment.
- **Safety:** The safety endpoint is the percentage of patients who experience one or more serious device -related adverse events during the first 3 months following AVF creation.

Additional exploratory analysis:

- Rate of serious procedure-related events will be reported at 3 months.
- Rate of serious device-related event rate will be reported at 3 months.
- Rate of device and/or procedure-related infections at 3 months.
- Arterial and arterialized vein flow rates and diameters will be measured via DUS at 30-45 Days and at each available follow-up visit post index procedure.

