4 STUDY SCREENING AND FOLLOW-UP PROCEDURES

Patients are required to undergo a thorough screening evaluation prior to the index procedure and return for evaluations according to the study follow-up schedule indicated in Table 1. Study data will be collected on case report forms (CRFs) provided by the Sponsor. Any site's standard of care tests may be done outside of the study (e.g., prior to study participation).

Table 1: Schedule of Study Procedures

Assessment	Screening	Index Procedure	Post Index Procedure				
			1-7 Days	30-45 Days	3 Months	6 Months (Optional) ¹	12 Month (Optional) ¹
Compliance window	-30 days	Day 0	1-7 days	30-45 days	Anniversary date + 14 / -7 days	Anniversary date + 45 / -15 days	Anniversary date + 60 / -30 days
Informed Consent	X						
History, Physical Exam, Laboratory Evaluation	X						
Ultrasound Evaluation	X	X ¹	X	X	X	X ¹	X ¹
Angiography/Venography	X ¹	X	X ¹	X ¹	X	X ¹	X ¹
Adverse Events		X	X	X	X	X	X
Dialysis Access Data				X ²	X ²	X ²	X ²

¹ Optional visit at the discretion of the Primary Investigator
² Will be obtained after dialysis is initiated using endoAVF created by the everlinQ System.

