4.4.1 Unscheduled Visit

In addition to scheduled follow-up visits, the patient should be instructed to contact the Investigator at any time during the follow-up period if he/she has questions or concerns relating to the procedure or the endoAVF. If the patient returns to the clinic for evaluation related to his/her participation in the study, an Unscheduled Visit evaluation should be performed and this data should be recorded on the Follow-Up Visit Case Report Form.

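### Time to Fistula Maturation is a day count, but maturation by duplex is seen only at scans 39 to 75 days apart, so duplex-dated times cluster at visit windows and run late

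*Combined protocol and SAP*

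**What the plan says.** Section 3.3 (Study Endpoints) counts Time to Fistula Maturation as "the number of days between the date of AVF creation and the date of endoAVF maturation". Maturation can be met in two ways. One is by scan: no stenosis or thrombosis, brachial artery flow of 500 ml/min or more, and the vein criterion. The other is use for dialysis. The last part of the definition reads "at least 4 mm vein diameter (as measured by duplex ultrasound) OR patient was dialyzed using 2 needles". No rule says how the date is set under either route.

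In section 4, the Table 1 row "Ultrasound Evaluation" requires post-procedure scans at days 1-7, days 30-45 and 3 months. The 3-month window is "Anniversary date + 14 / -7 days". The 6- and 12-month scans carry the footnote "Optional visit at the discretion of the Primary Investigator". Dialysis access data carry a different footnote: "Will be obtained after dialysis is initiated using endoAVF created by the everlinQ System". For unscheduled visits, section 4.4.1 says that "an Unscheduled Visit evaluation should be performed and this data should be recorded on the Follow-Up Visit Case Report Form", but it does not require a scan.

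Section 3.3 promises descriptive statistics with no hypothesis tests and names Kaplan-Meier only for primary and secondary patency. Section 5 (Data Analysis) summarises continuous variables by mean, standard deviation, median, minimum and maximum.

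**The concern.** A fistula crosses the flow and diameter thresholds on some unobserved day between two scans. If the date of the first qualifying scan is taken as the maturation date, the recorded time cannot be earlier than the true one and is usually later. Its value then depends heavily on when the visit was booked. The default summaries in section 5 would treat these dates as exact.

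Two consequences follow. The mean and median days partly describe the visit calendar, so they are a weak answer to how fast the endoAVF matures. Subjects are also not comparable with each other: one who happens to have an early unscheduled scan, or who is already on dialysis and is needled early, looks faster than an identical subject who waits for the 3-month scan. Section 2.1 raises the prospect of better maturation than historical data, and a delay created by the schedule would distort such a comparison.

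This concerns subjects who do mature. How never-matured subjects enter the summary is a separate gap.

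**Working it through.** The plan states no expected time to maturation and no calculation for this endpoint, so there is no figure to reproduce.

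**Inputs from the documents.** Required scans V0 in days 1-7, V1 in days 30-45 and V2 at 3 months. Taking 3 months as 91 days (an assumption), V2 runs from 91 − 7 = 84 to 91 + 14 = 105. The gap between V1 and V2 is therefore 84 − 45 = 39 to 105 − 30 = 75 days.

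**Assumptions.** Each visit is uniform in its window; once the criteria are met they stay met; the recorded day is the first required scan on or after the true day T. The distribution of T is assumed, because the documents give none for the endoAVF.

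**Hand check, T uniform on days 30-90, V1 uniform on 30-45, V2 fixed at day 91.**
- Share dated at V1 = E[V1 − 30]/60 = 7.5/60 = 12.5%.
- V1 contribution to the mean = E[V1(V1 − 30)]/60 = (30 × 7.5 + 75)/60 = 5.
- Recorded mean = 5 + 0.875 × 91 = 84.6, against a true mean of 60: a delay of 24.6 days.

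**Hand check, fast maturation, T uniform on days 7-30.** Everyone is dated at V1. Recorded mean = 37.5, true mean = 18.5, delay = 19.0 days.

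**Hand check, T uniform on days 7-60, V2 uniform on 84-105 (mean 94.5).**
- Share dated at V1 = (37.5 − 7)/53 = 57.5%.
- E[V1²] = 37.5² + 15²/12 = 1425, so the V1 contribution is (1425 − 7 × 37.5)/53 = 21.9.
- The V2 contribution is (22.5/53) × 94.5 = 40.1.
- Recorded mean = 62.1 against a true 33.5, a delay of about 29 days. The recorded median is about 43.

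**Simulation, duplex only, full windows, 1,000,000 draws each** (true means are among subjects seen mature by the 3-month scan):

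| Assumed true maturation | True mean | Recorded mean | Recorded median | Mean delay |
|---|---|---|---|---|
| Uniform 30-90 | 59.6 | 87.7 | 93.2 | 28.1 |
| Uniform 7-90 | 48.1 | 73.6 | 88.5 | 25.5 |
| Uniform 7-45 | 26.0 | 49.3 | 40.2 | 23.3 |
| Uniform 7-30 | 18.5 | 37.5 | 37.5 | 19.0 |
| Exponential, mean 30 | 25.7 | 48.1 | 39.5 | 22.4 |
| Exponential, mean 60 | 35.3 | 58.9 | 42.8 | 23.5 |
| Lognormal, median 45, sigma 0.5 | 45.8 | 73.1 | 88.1 | 27.3 |
| Lognormal, median 60, sigma 0.4 | 57.3 | 86.7 | 93.1 | 29.5 |

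For uniform 30-90, 73% of times are at least 14 days late. With fixed visits the mean delay is 27.0 (days 30 and 84), 24.3 (days 37.5 and 91) or 30.0 (days 45 and 105).

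**Narrower cohorts.** If all subjects mature between the two windows, every one is dated at V2. Uniform 46-60 (true mean 53) and uniform 60-80 (true mean 70) both record a mean and median of 94.5, with delays of 94.5 − 53 = 41.5 and 94.5 − 70 = 24.5 days. Uniform 60-90 with V2 fixed at day 91 gives 91 − 75 = 16 days. The 19-30 range describes the broader distributions and is not a bound.

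**Adding the two-needle route.** Take uniform 30-90 and suppose that a share of subjects has two-needle dialysis 0-28 days after true maturation, with the earlier of dialysis and scan recorded. Share and lag are both assumed.

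| Share with two-needle dialysis | Mean delay (days) |
|---|---|
| 0% | 28.1 |
| 25% | 23.9 |
| 50% | 19.7 |
| 75% | 15.6 |
| 100% | 11.5 |

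Where the dated session is itself the event, the delay is zero.

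**The case against.** The strongest reply is that the documents do not establish the size of the delay. The only maturation course they give, "Over the course of the following 1 - 3 months, the AVF gradually matures", is in the Introduction's account of traditional surgery. It refers to flow sufficient for hemodialysis and not to this study's thresholds. That stands: nothing in the plan says when an endoAVF matures.

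Second, two-needle dialysis has its own calendar date and the study enrols patients who need hemodialysis, so part of the endpoint may not be visit-dated. This also stands, although pre-dialysis patients are eligible (section 3.5.1) and can qualify only by duplex until dialysis starts.

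Third, section 5 gives its mean-and-median rule with examples such as age and weight and does not name this endpoint. True, but section 3.3 promises descriptive statistics for all endpoints and offers no other method for this one.

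Fourth, this is a pilot of up to 50 subjects with no tests, and a reader who knows the windows could interpret a visit-dated median. That limits the harm but does not remove the delay, and pooling scan dates with dialysis dates makes the median hard to interpret even for such a reader.

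A reader might infer that the recorded median is fixed at about day 91 whatever the true speed. The documents do not support this. It needs nearly all maturation to fall after day 30 and the 3-month visit to be on one fixed day. With maturation over days 7-60 the recorded median is about 43, and over days 7-45 about 40.

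**Conclusion.** The point holds for subjects who qualify by duplex: their recorded time is in effect the first qualifying scan, it clusters in the visit windows, and it overstates the true time. With duplex only, the mean delay is about 19 to 30 days across the broader distributions tried, fast and slow. With 25% to 100% having two-needle dialysis within 28 days of maturation, it is about 24 down to 11.5 days. The exact delay and the recorded median depend on an unstated maturation course, the two-needle share and lag, and where visits fall in their windows.

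A reader might infer that every recorded time follows the visits, or that the whole endpoint is known to be about four weeks late. Neither follows, because the two-needle route, unscheduled scans and the optional 6- and 12-month scans all supply other dates. No test, decision rule or sample size depends on this endpoint. The harm is to one descriptive estimate, and it is cheap to avoid.

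**What to change.** In section 3.3:

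1. Make the main summary the cumulative percentage matured by the 30-45 day visit and by the 3-month visit, and by later visits where done. Split by pre-dialysis and on-dialysis status if numbers allow, as section 3.3 already plans for catheter exposure.
2. If a time distribution is wanted, treat maturation as interval-censored. The lower limit is the last non-mature scan (or the date of creation if there is none). The upper limit is the earlier of the first mature scan and the first two-needle dialysis through the endoAVF. Use, for example, the Turnbull estimator. The dialysis date is an upper limit and not an exact time, because the scan criteria may have been met before it.
3. Right-censor subjects not yet mature at their last scan.
4. Do not report mean or median days as if exact.

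The cost is some wording and one standard analysis, with no extra visits or scans. CRF content is not in the documents, so confirm that it captures the date and result of every scan, including unscheduled ones, and the date of first two-needle use. The downside is that a single days-to-maturation figure becomes a by-visit percentage or a range. With at most 50 subjects and few scheduled looks, the Turnbull curve will add little to the percentages, so the first item matters most.

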3.5.2 Exclusion Criteria

1. Known central venous stenosis or central vein narrowing $> 50\%$ based on imaging on the same side as the planned AVF creation.
2. Upper extremity venous occlusion(s) and/or vessel abnormality(ies) on the same side as the planned AVF creation that precludes endovascular AVF creation by everlinQ System as deemed by the interventionalists' clinical judgment.
3. Prior surgically created access in the planned treatment location.
4. Functioning surgical access in the planned treatment arm.
5. Pregnant women.
6. New York Heart Association (NYHA) class III or IV heart failure.
7. Hypercoagulable state.
8. Known bleeding diathesis.
9. Immunosuppression, defined as use of immunosuppressive medications used to treat an active condition.
10. Documented history of drug abuse including intravenous drugs within six months of AVF creation.
11. "Planned" concomitant major surgical procedure within 6 months of enrollment or previous major surgery within 30 days of enrollment.
12. Currently being treated with another investigational device or drug.
13. Known allergy to contrast dye which cannot be adequately pre-medicated.

14. Known adverse effects to sedation and/or anesthesia which cannot be adequately pre-medicated.
15. Patients who do not have an ulnar or radial artery.
16. At the time of procedure distance between target artery and vein will not allow magnets to align vessels sufficiently to create the fistula.
17. Evidence of active infections on the day of the index procedure.
18. Written informed consent not obtained.

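### The catheter-exposure endpoint is named as a duration but defined as a rate of use at visits, and the plan collects no catheter dates from which a duration could be calculated

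*Combined protocol and SAP*

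**What the plan says.** Section 3.3 (Study Endpoints) names one endpoint "Duration of Central Venous Catheter Exposure". Its definition is "The rate of CVC use per enrolled subjects at 30-45 Days and other follow-up visits". The next sentence splits it by dialysis status: "The analysis will be performed for pre-dialysis and on dialysis patients, as applicable". The entry just before it, time to fistula maturation, is defined as "the number of days between the date of AVF creation and the date of endoAVF maturation".

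Table 1 in Section 4 has no row for central venous catheters. The nearest item is Dialysis Access Data, scheduled at 30-45 days and at 3, 6 and 12 months. The last two visits are optional at the investigator's discretion. A footnote qualifies that item at every visit: "Will be obtained after dialysis is initiated using endoAVF created by the everlinQ System".

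Section 4.4.1 puts unscheduled visits on the follow-up form and does not mention catheter dates. Section 5 (Data Analysis) describes general summary statistics and does not refer to this endpoint.

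**The concern.** The name promises time on a catheter; the definition delivers a proportion of subjects at a few visits. These are different quantities, and the second does not yield the first. The neighbouring maturation endpoint is defined as a count of days between two dates, so the plan does specify days where it means days.

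Time on a catheter matters to patients. Section 1 says: "Catheters are associated with higher morbidity, mortality, and costs and are therefore considered a last resort". A report that gives visit proportions under the heading of duration could be read as stating how long subjects were exposed, when the data would fit very different exposures.

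There is also a question of whether the data will exist. If access data start only once the endoAVF is in use for dialysis, the subjects with most catheter exposure are the ones most likely to lack a scheduled record.

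**Working it through.** The plan gives no figure for this endpoint, so there is none to reproduce. The check has four parts.

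**1. Name against definition.** A duration needs a start and an end. Sections 3.3, 4 (Table 1), 4.4.1 and 5 provide for no insertion date, removal date, count of catheter-days or time to removal.

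**2. Spacing of visits.** Inputs from Table 1: the second post-procedure visit falls on days 30 to 45, and the 3-month window is "Anniversary date + 14 / -7 days". Assumption: 3 months = day 91.

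- 3-month window: 91 − 7 = 84 to 91 + 14 = 105.
- Shortest interval from the 30-45 day visit: 84 − 45 = 39 days.
- Longest interval: 105 − 30 = 75 days.

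A catheter present at the first visit and gone at the second could have come out at any point in that interval, with the same score.

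**3. How far two visit rates pin down mean duration.** Assumed example, not from the documents: 50 subjects, all with a catheter at day 0, one unbroken spell each, 20 still using it at day 37 and 10 at day 91. The visit rates are 20/50 = 40% and 10/50 = 20%. Over days 0 to 91:

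| Group | n | Fewest days each | Most days each |
|---|---|---|---|
| Out by day 37 | 30 | 0 | 37 |
| In at day 37, out by day 91 | 10 | 37 | 91 |
| In at day 91 | 10 | 91 | 91 |

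- Minimum mean: (30×0 + 10×37 + 10×91)/50 = 1280/50 = 25.6 days.
- Maximum mean: (30×37 + 10×91 + 10×91)/50 = 2930/50 = 58.6 days.
- Ratio: 58.6/25.6 ≈ 2.3.

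Identical reported rates therefore fit a more than twofold range in the named quantity.

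**4. Spells between visits, and subjects without a record.** The text does not say whether use means status on the visit day or any use since the last visit. On the first reading, with visits on days 45 and 84, a catheter in place from day 46 to day 83 (83 − 46 = 37 days) scores zero at both, unless an unscheduled visit catches it. On the second reading it is counted, but its length is still unknown.

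The endpoint divides by enrolled subjects, whereas the Table 1 footnote restricts access data to those who have begun dialysis through the endoAVF. A subject still dialysing by catheter at 3 months belongs in the denominator and should be in the numerator, yet may have no scheduled access data. No rule for such missing values is given.

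**The case against.** The strongest reply is that this is one of eight descriptive endpoints in a single-centre pilot with no hypothesis tests. Renaming it as catheter use at follow-up visits would remove the contradiction at no cost. That is fair on severity: no primary conclusion, error rate or sample size depends on it. But renaming alone gives up the quantity that the plan set out to report, and it leaves the collection gap in Table 1.

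A second reply is that use may be meant cumulatively, and that unscheduled visits may pick up catheters placed and removed between scheduled ones. This stands as far as it goes: the missed-spell point holds only on the status-at-visit reading. It does not rescue duration, because neither route supplies dates. The case report forms are not among the documents and might hold such dates, but the plan does not call for them.

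A reader might also infer that subjects who leave a failed endoAVF for a graft or surgical fistula are miscounted as catheter-free. The documents do not support that. A subject dialysing through a graft or surgical fistula without a catheter is in fact catheter-free, and one moved to a catheter counts as using it. Failure of the endoAVF is covered by the maturation and patency endpoints. Nor does the plan say that a missing access record is to be read as no catheter, so the footnote creates missing data, not a documented bias in a known direction.

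**Conclusion.** The point holds in a limited form. Name and definition disagree, and the plan as written cannot report duration of catheter exposure; this rests on the text alone. The size is illustrative: visit intervals of 39 to 75 days depend on taking 3 months as day 91, and the range of 25.6 to 58.6 mean catheter-days depends on the assumed example with one spell per subject. That catheters between visits go unseen is conditional on a reading that the text leaves open. The collection gap follows from the Table 1 footnote, although catheter status might be recorded elsewhere on forms that are not shown. The endpoint should be corrected, but nothing confirmatory turns on it.

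**What to change.** - **Data.** Record insertion and removal dates for every central venous catheter, including any in place at the index procedure, and current access type for all enrolled subjects at each visit. Amend the Table 1 footnote on Dialysis Access Data so that collection no longer waits for dialysis through the endoAVF.
- **Endpoint.** Define exposure as catheter-days from the index procedure (from dialysis start for pre-dialysis subjects) to 3 months, with follow-up ending at death, transplant or study exit. Report it with days at risk as the denominator, for example as the proportion of at-risk days with a catheter. The denominator matters: a subject who dies on day 37 with a catheter throughout and one whose catheter comes out on day 37 but who is followed to day 91 both contribute 37 catheter-days, yet the proportions are 37/37 = 100% and 37/91 ≈ 41%.
- **Visit rate.** Keep it as a separate, plainly named measure of catheter use at each visit, state whether it means status on the day or use since the last visit, and show it by current access type as description only.

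The cost is two date fields, one access-type field, revised wording and slightly more data entry. That the dates can be obtained from dialysis records is an assumption; if they are not captured prospectively, they may not be recoverable at analysis.
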